4.1 Subject Identification

Patient confidentiality will be maintained in accordance with Health Information Portability and Accountability Act (HIPAA) guidelines. All participants must sign an informed consent that will describe the objectives of the study and potential risks. All patient data reported on the case reports forms will be

identified by the patient's initials and study code number only. Patients shall not be identified by name. This should serve to protect the confidentiality of subjects enrolled on the trial. Clinical data and records for all subjects studied including history and physical findings, laboratory data, and results of interventions are to be maintained by the investigators in a secure, locked location. Computerized data will require password authorization(s) for access.

4.2 Description of the Recruitment Process

Potential subjects will be identified at the time of consultation in the Department of Radiation Oncology or in the Precision Medicine Center of Excellence for prostate cancer.

4.3 Description of the Informed Consent Process

Only the principal investigator or those listed as co-investigators will perform the informed consent interview. The informed consent interview will take place before the patient is to be treated to ensure that the patient has adequate time to discuss the research project with family, friends, and/or other Health Care providers. During the informed consent interview, the interviewer (investigator) will take as much time as needed to ensure that the potential subject understands the research project and also clearly understands that he does not have to participate in this project to receive his cancer treatment at Johns Hopkins.

4.4 Subject Assignment

We will enroll 30 patients onto the trial in order to ensure at least 24 evaluable patients.

This will be a two-arm study with randomization. We will apply 2:1 randomization to treatment (Flu) vs placebo arm available and to confirm Flu-induced increase in γ H2AX foci vs control. All patients would receive standard androgen suppression and brachytherapy in accordance with their disease parameters and risk stratification.

The measurement of Flu may be accordingly transformed to ensure the necessary distributional and model assumptions are met. Analyses for all secondary endpoints will be exploratory in nature, and specified in detailed in the study protocol and statistical analysis plans.

4.5 Clinical Assessments / Study Calendar A

In order to minimize the need for research-only in-person visits, telemedicine visits may be substituted for in person clinical trial visits or portions of clinical trial visits where determined to be appropriate and where determined by the investigator not to increase the participants' risks. Prior to initiating telemedicine for study visits the study team will explain to the participant, what a telemedicine visit entails and confirm that the study participant is in agreement and able to proceed with this method. Telemedicine acknowledgement will be obtained in accordance with the Guidance for Use of Telemedicine in Research. In the event telemedicine is not deemed feasible, the study visit will proceed as an in-person visit. Telemedicine visits will be conducted using HIPAA compliant method approved by the Health System and within licensing restrictions.

A synopsis of the study procedures is shown below:

Parameter	Pre-Study	Pre-androgen suppression	PRE-BIOPSY / IMPLANT			BIOPSY / IMPLANT DAY ^A	POST-BIOPSY / IMPLANT	
			-180 to 0 DAYS ^G	-10 to 0 DAYS	-12 TO -6 HOURS		4 weeks (+/-7 days)	6 months (+/-45 days)
H&P, LABS (CMP)	X							
Study Eligibility	X							
MRI of prostate	X							
Androgen suppression w/ GnRH analogue	X ^G		X ^G					
Study Drug Admin (250mg vs Placebo)					X			
LABS (PSA / Testosterone)	X		X ^{C, H}				X	X
Plasma for cell free DNA ^B		X ^D		X ^{C, D}			X ^D	X ^D
Urine (50 mL)		X ^D		X ^{C, D}			X ^D	X ^D
Plasma for hydroxyflutamide ^F				X ^E		X		

^A Day of biopsy and brachytherapy implant procedure.

^B Streck Tubes (10 mL) x 4

^C Samples may be obtained either pre- or post-flutamide ingestion, but prior to biopsy/implant

^D These items are separate (optional) consent for exploratory analysis.

^E -10 to 0 Day Timepoint for non-randomized cohort (n=6) only; sample taken prior to hydroxyflutamide ingestion

^F Heparin/Green Top Tubes (4 mL) x 1

^G Patient may be enrolled already on GnRH analogue, or receive after enrollment. Brachytherapy to be performed anytime within 180 days from initiation of androgen suppression provided the patient's testosterone level is < 50 ng/dL.

^H PSA and Testosterone should be done at least 30 days after Initiation of Androgen Suppression and within 180 days prior to brachytherapy.

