2.0 Study Objectives

Primary objective:

To confirm DNA double strand breaks occur in prostate cancer tissue following pulse-dose Flutamide administration in patients who are androgen suppressed, as compared to control patients receiving placebo.

Exploratory objective:

To explore the feasibility of detecting cancer-specific alterations in DNA methylation and structure within urine and plasma, and the kinetics for these measures when compared with PSA values and clinical response. We will examine whether prostate cancer specific DNA methylation alterations at a panel of frequently hypermethylated loci (e.g. GSTP1, PTGS2, MDR1, APC, RARbeta, gene promoters) can be used as a DNA based biomarker for tracking therapeutic response.

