*** ADDITIONAL IMPORTANT NOTES ON NEXT PAGE OF PROTOCOL ***

Important notes:

- Timing of brachytherapy
 - Brachytherapy to be performed anytime within 180 days from initiation of androgen suppression provided the patient's testosterone level is < 50 ng/dl.
- Patient will be **off-protocol** if **serum testosterone at 0-7 days prior to implant is above castrate level (>50 ng/dL or >1.7 nmol/L)**
- Approximately **1/3 of each subject's total biopsy material will be frozen** for future laser capture RNA sequencing

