5.2.2 Serum and urine exploratory analyses

For purposes of exploratory analyses, serum and urine samples will be collected pre-androgen suppression, post-androgen suppression, 1-month post-implant, and 6-month follow-up times. Patients will be asked to sign consent specifically for these samples, otherwise they have the choice to opt out. Given that these analyses do not affect the primary endpoint, patients opting out of the exploratory serum and urine analyses will not adversely affect the study endpoint.

For each urine and plasma sample, the qMBD-seq approach ([name] 2011) will be used to determine the MI and SR scores to assess levels of cancer specific DNA methylation and structural alterations, and the kinetics for these measures will be determined at the timepoints collected and compared with PSA values. As a part of the exploratory analysis consent, patients will also be consented to allow access to any subsequent biopsy and corresponding PSA that may be obtained through standard clinical care, to look at the relationship of these markers.

This analysis will help us to explore the feasibility of detecting cancer-specific alterations in men with prostate cancer. We will also examine whether prostate cancer specific DNA methylation alterations at a panel of frequently hypermethylated loci (e.g. GSTP1, PTGS2, MDR1, APC, RARbeta, gene promoters) can be used as a DNA based biomarker for tracking therapeutic response using our highly sensitive COMPARE-MS DNA methylation assay.

Blood collection

In most cases, blood samples will be drawn from patients scheduled to have venipuncture for routine clinical purposes. In some cases, when this is not possible, blood draws will occur at times other than those needed for routine clinical care. Generally, blood draws for research purposes will be 4 tablespoons of blood (amounts to 4 x 10mL tubes).

Blood Processing. Generally, the processing and storage of blood samples will involve the following: blood will be drawn into 4 Streck tubes for collection and stored as plasma, serum, white blood cells or whole blood. Serum will be separated from other cellular components by centrifugation, allocated into tubes, catalogued, and frozen at -70 to -80° C or viably in liquid nitrogen freezers. Samples may be processed for DNA, RNA, and/or protein. Specimens will be barcoded for inventory management and for tracking clinical study usage.

Urine collection and processing

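### The on-suppression PSA and the pre-implant DNA samples it is compared with may be drawn anywhere from 0 to 150 days apart

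*Combined protocol and SAP*

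**What the plan says.** Section 2.0 sets an exploratory objective that covers "the kinetics for these measures when compared with PSA values and clinical response". Section 5.2.2 turns this into an analysis of the MI and SR scores: "the kinetics for these measures will be determined at the timepoints collected and compared with PSA values".

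The sampling times are in the Section 4.5 calendar:

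- **PSA and testosterone** share one row. The only on-suppression, pre-implant entry is in the -180 to 0 day column. The -10 to 0 day, -12 to -6 hour and implant-day cells of that row are empty. Footnote H reads: "PSA and Testosterone should be done at least 30 days after Initiation of Androgen Suppression and within 180 days prior to brachytherapy".
- **"Plasma for cell free DNA" and urine** have their pre-implant entry in the -10 to 0 day column. Their -180 to 0 day cells are empty.
- **Footnote C** is attached to all three of these entries: "Samples may be obtained either pre- or post-flutamide ingestion, but prior to biopsy/implant".
- **Footnote G** limits the interval from suppression to implant: "Brachytherapy to be performed anytime within 180 days from initiation of androgen suppression provided the patient's testosterone level is < 50 ng/dL".

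The important notes after the calendar take a patient off protocol if "serum testosterone at 0-7 days prior to implant is above castrate level". That note does not mention PSA.

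No section requires the PSA to be drawn with the plasma and urine, sets a maximum interval between them, or says how unequal dates are to be handled.

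**The concern.** PSA is the yardstick for the new DNA measures. If the two come from different stages of suppression, a disagreement between them may reflect only the difference in dates. The permitted gap also grows with the time each man spends on suppression before his implant, so the mismatch can differ between men. With about 30 men enrolled and the samples optional, it cannot be assumed to average out.

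The pre-implant sample is the only one showing the markers under suppression before biopsy and implant disturb the gland. Footnote G also lets men enroll when already on a GnRH analogue, and Section 15.2 bars study procedures before consent. Those men cannot give a pre-suppression research sample under this protocol, so for them the pre-implant pair is the first one available.

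A PSA that was not drawn at the time cannot be recovered later by analysis.

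**Working it through.** The documents state no interval between PSA and DNA sample, so there is no figure to reproduce. The permitted interval follows from the calendar by date arithmetic.

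**Inputs** (implant = day 0; all from Section 4.5)

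- Suppression starts on day -D, with D at most 180 (footnote G).
- PSA is drawn on day p, with p from -D + 30 to 0 (footnote H).
- Plasma and urine are drawn on day q, with q from -10 to 0 (calendar column).

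**Formula**

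Gap = |p - q|. The smallest value is always 0, when both are drawn on the same day. The largest value comes from the earliest permitted PSA (p = -D + 30):

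- DNA sample on day 0: gap = D - 30
- DNA sample on day -10: gap = D - 40

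If the PSA is drawn after the DNA sample, the gap cannot exceed 10 days.

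**Results**

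| Suppression started (days before implant) | Earliest permitted PSA | Largest gap, DNA on day 0 | Largest gap, DNA on day -10 |
|---|---|---|---|
| 60 | day -30 | 30 | 20 |
| 90 | day -60 | 60 | 50 |
| 120 | day -90 | 90 | 80 |
| 150 | day -120 | 120 | 110 |
| 180 | day -150 | 150 | 140 |

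The column label alone would suggest a PSA as early as day -180. Footnotes G and H together rule that out: 180 - 30 = 150, so the usable window is day -150 to day 0.

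**If PSA were drawn with the 0-7 day testosterone**

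Then p lies between -7 and 0 and q between -10 and 0. The largest gap is |0 - (-10)| = 10 days.

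**Comparison with the other visits**

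At 4 weeks and 6 months, PSA, plasma and urine are in the same calendar columns, so one visit serves all three. At baseline they are not: PSA is under Pre-Study and the DNA samples are under Pre-androgen suppression, with no stated maximum interval. The pre-implant point is therefore not the only loose pairing, but it is the one for which the documents give enough dates to bound the gap.

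**The case against.** The strongest reply is that a near-implant PSA is probably drawn anyway. The important notes presuppose a testosterone 0-7 days before implant, PSA and testosterone share one calendar row, and footnote C lets that row's sample be taken right up to the implant. If practice follows this, the gap is at most 10 days. This stands as a statement about likely practice. It does not settle the text: the note names testosterone only, footnote C permits a shared draw without requiring one, and footnote H allows the joint draw to be much older.

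A second reply is that Section 5.2.2 compares kinetics, which can be done with dated values at unequal times. That also stands in part. A reader might infer that the plan promises same-day pairs at every sampling time, but neither Section 2.0 nor Section 5.2.2 says so, and no agreement statistic is specified. Section 4.6 has clinical results, PSA among them, abstracted from source records, so the gap should be visible at analysis and other routine values may exist. None of this guarantees a PSA close to the DNA sample.

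A reader might also infer a large multiplicative error in PSA. The documents do not support one. It would need a rate of PSA decline on suppression and a nadir or assay floor, and none of these is given.

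Finally, the samples are optional (footnote D), the aim is to explore feasibility, and no test, sample size or stopping rule uses this pair. That is correct and limits the weight of the point.

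**Conclusion.** The calendar permits a gap of 0 to 150 days between the on-suppression PSA and the pre-implant plasma and urine, although PSA is the stated comparator. The date arithmetic rests only on footnotes G and H and the calendar columns. That the gap matters rests on one assumption not stated in the documents: that PSA is not constant between day 30 of suppression and the implant.

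150 days is the maximum, reached only when suppression runs the full 180 days, the PSA is drawn at day 30 of suppression and the DNA sample is taken on the day of implant. It should not be read as the usual gap. The documents give no distribution of suppression times or PSA dates, so the typical gap is unknown.

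The effect is confined to the optional exploratory analysis. The primary gammaH2AX endpoint, the run-in decision and the feasibility stopping rule do not use PSA. This is a low-priority improvement that is cheap before sampling and cannot be made afterwards.

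**What to change.** 1. In the Section 4.5 calendar, for men who consent to the exploratory samples, add a PSA to the -10 to 0 day research draw. Taken from the same venipuncture, it makes the gap 0. If it is more practical to draw it with the 0-7 day testosterone, the gap is at most 10 days.
2. In Section 5.2.2, name that PSA as the pre-implant comparator. Keep any earlier on-suppression PSA as a separate point with its own date.
3. Reconcile footnote H with the important note on testosterone 0-7 days before implant, so that the calendar shows which draw each refers to. Which window should govern the castration check is for the investigators to decide and is not part of this point.

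The cost is one extra serum tube and one assay per consenting man, at a draw that is already scheduled, plus one calendar cell and one sentence in Section 5.2.2. Treatment is unchanged.

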*** ADDITIONAL IMPORTANT NOTES ON NEXT PAGE OF PROTOCOL ***

Important notes:

- Timing of brachytherapy
 - Brachytherapy to be performed anytime within 180 days from initiation of androgen suppression provided the patient's testosterone level is < 50 ng/dl.
- Patient will be **off-protocol** if **serum testosterone at 0-7 days prior to implant is above castrate level (>50 ng/dL or >1.7 nmol/L)**
- Approximately **1/3 of each subject's total biopsy material will be frozen** for future laser capture RNA sequencing

4.6 Data to be collected

The data that will be collected for this trial will be the results and/or findings of the procedures and assessments that are outlined in 4.5 and 4.6. Results/findings will also be abstracted from the source documents and records (e.g. clinic notes, radiology reports, lab reports, and recorded onto either study specific case report forms or within electronic database housed on the secure Radiation Oncology network drive. The data manager assigned to this trial will be responsible for the data collection with regard to clinical elements (PSA, etc.). The principal investigator or coinvestigators and/or assistants may also be responsible for collection and analysis of dosimetric and imaging data. Both data managers and/or investigators will have access to patient medical records and will record medical information from the medical record onto the relevant case report forms or database. The principal investigator will review the data on a quarterly basis for accuracy.

5.0 Research Interventions

Patients who will be offered this protocol are those who are currently offered brachytherapy as standard treatment at our institution.

5.1 Pre-implant Flutamide vs placebo dosing

Patients will receive either Flutamide single 250mg dose or placebo, taken orally 6-12 hours prior to the brachytherapy.

5.2 Plasma, urine and serum sampling for analyses

5.2.1 Plasma assay for 2-hydroxyflutamide

2-hydroxyflutamide levels will be assayed both pre- and post-flutamide dosing in the initial non-randomized cohort. For the randomized cohort, only post-flutamide levels of 2-hydroxyflutamide will be assayed.

Blood samples (~4 ml) will be drawn into heparinized test tubes 0-10 days before drug administration (non-randomized initial cohort only), and also at 6-12 hours post-ingestion of Flutamide. Blood samples are to be immediately placed on ice after collection and centrifuged at 1300g for 10 minutes at 4 degrees C, and the plasma fraction to be separated and stored in polypropylene tubes at temp of -70 degrees C until analysis.

For analysis, specimens will be transferred to Analytical Pharmacology Core Laboratory and analyzed based on method described by Niopa et al.⁷

5.2.2 Serum and urine exploratory analyses

For purposes of exploratory analyses, serum and urine samples will be collected pre-androgen suppression, post-androgen suppression, 1-month post-implant, and 6-month follow-up times. Patients will be asked to sign consent specifically for these samples, otherwise they have the choice to opt out. Given that these analyses do not affect the primary endpoint, patients opting out of the exploratory serum and urine analyses will not adversely affect the study endpoint.

For each urine and plasma sample, the qMBD-seq approach ([name] 2011) will be used to determine the MI and SR scores to assess levels of cancer specific DNA methylation and structural alterations, and the kinetics for these measures will be determined at the timepoints collected and compared with PSA values. As a part of the exploratory analysis consent, patients will also be consented to allow access to any subsequent biopsy and corresponding PSA that may be obtained through standard clinical care, to look at the relationship of these markers.

This analysis will help us to explore the feasibility of detecting cancer-specific alterations in men with prostate cancer. We will also examine whether prostate cancer specific DNA methylation alterations at a panel of frequently hypermethylated loci (e.g. GSTP1, PTGS2, MDR1, APC, RARbeta, gene promoters) can be used as a DNA based biomarker for tracking therapeutic response using our highly sensitive COMPARE-MS DNA methylation assay.

Blood collection

In most cases, blood samples will be drawn from patients scheduled to have venipuncture for routine clinical purposes. In some cases, when this is not possible, blood draws will occur at times other than those needed for routine clinical care. Generally, blood draws for research purposes will be 4 tablespoons of blood (amounts to 4 x 10mL tubes).

Blood Processing. Generally, the processing and storage of blood samples will involve the following: blood will be drawn into 4 Streck tubes for collection and stored as plasma, serum, white blood cells or whole blood. Serum will be separated from other cellular components by centrifugation, allocated into tubes, catalogued, and frozen at -70 to -80° C or viably in liquid nitrogen freezers. Samples may be processed for DNA, RNA, and/or protein. Specimens will be barcoded for inventory management and for tracking clinical study usage.

Urine collection and processing

Urine collected from patients is known to contain nucleic acid material that could serve as a biomarker for cancer. In addition, urine studies may involve purification of proteins and/or cells. Urine is self-collected. Sterile cups will be provided by the clinic.

In [name] laboratory, urine preservative (Norgen BioTEK Corp, Cat # 18124) will be added to the urine and stored at room temperature or 4 degrees C until further processing.

Purification of Nucleic Acid from biospecimens (urine/plasma):

DNA purification from plasma and urine will be accomplished using a commercially available Qiagen virus vaccum kit. (QiaVirus vaccum kit, Cat # 57714). Starting with 1 ml of plasma or 10 ml of urine prepared as detailed above (thawed @ RT). The procedure for plasma is described below. Similar column purification method will be used for urine with the notable difference of a larger input volume due to relative scarcity of nucleic acid. Briefly, we will transfer 500 µl plasma to two separate 2 ml tubes, add 40 µl Proteinase K and

mix by vortexing, add 5.6 μ l 1 μ g/ μ l RNA carrier to 500 μ l and mix by vortexing. The specimen will be incubated at 1 h @ 60°C in heating block, then cooled on ice before adding 600 μ l EtOH, mixed thoroughly by vortexing and incubated 5 min at room temperature. The sample (lysate) will be transferred to a vacuum purification column w/extension tube placed on a vacuum manifold. The column will be washed to purify the nucleic acids before the eluate drawn off the column in nuclease free molecular biology grade water (~100ul). *qMBD-seq*: The qMBD-seq approach involves division of DNA extracted from each plasma and urine sample into two fractions: a total input fraction, from which structural alterations can be measured, and a methyl-binding domain (MBD)-enriched methylated fraction, from which DNA methylation changes can be measured (see Figure 1). Briefly, each DNA sample from urine or plasma will be spiked in with a fully methylated lambda-phage DNA internal control, fragmented, and ligated to barcoded sequencing adaptors. Half the sample will be set aside as the total input, and the other half will be subjected to enrichment of methylated DNA using MBD-conjugated magnetic beads as we have described previously^{8, 9–11}. The resulting enriched methylated fraction and the total input fraction will then be amplified, and the resulting libraries will be subjected to 50x50 bp paired end next generation sequencing. In each fraction, the number of reads mapping to each of 350 regions that we have previously shown to be highly recurrently (>80% of prostate cancers), and stably (maintained through the disease course and across metastatic dissemination) methylated in a prostate cancer specific manner (see Figure 2) will be determined. The number of reads mapping to the fully methylated spiked-in internal quantitation standard will also be determined. The MI score will be defined as: $MI = (H_E/H_T)/(S_E/S_T)$, where H_E and H_T are the number of reads mapping to the prostate cancer specific hypermethylated regions in the enriched and total input fractions respectively, and S_E and S_T are the number of reads mapping to the spiked-in internal standard in the enriched and total input fractions respectively. Conceptually, this MI score is related to the amount of methylated DNA derived from the 350 regions that we have previously identified to be highly frequently and stably hypermethylated in human prostate cancer but not in any normal tissues assessed (including normal prostate, lymph nodes, spleen, liver, kidney, and blood). This approach essentially allows massively parallel assessment of all of these regions in a single assay. If in the future, we needed to include other regions or subtract regions, this can simply be done informatically without any changes needed to the actual assay. Furthermore, the number of paired end reads showing evidence of rearrangements (each sequence from a paired-end fragment mapping to discontiguous portions of the genome), determined as described previously^{12,13}, in the total input fraction normalized per million overall reads (SR score) will provide a parallel measure of the amount of DNA containing genomic rearrangements. By measuring these alterations using an unbiased genome-wide approach, we can be less limited by stochastic factors that can prevent assessment of a single locus. Furthermore, by measuring both the DNA methylation and structural alterations, we are less prone to technical issues that may limit measurement of any one of these alteration classes. Finally, assessment of both urine and plasma, both of which can be readily and non-invasively obtained, will allow a higher chance of detecting these alterations. The accuracy and precision of each type of analysis will be explored using prostate cancer cell line DNA spiked in a dilution series into normal plasma and urine.

A participant's care will not be altered if they choose to opt out of the exploratory plasma/urine analysis portion of the study.

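### MI and SR are relative measures described as amounts; reporting the spike-calibrated numerator and denominator of MI beside it would let a change in background DNA be told apart from a change in tumour DNA

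*Combined protocol and SAP*

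**What the plan says.** The laboratory steps and both scores are in Section 5.2.2 of the combined protocol and SAP.

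- DNA is purified from 1 mL of plasma or 10 mL of urine. Each DNA sample "will be spiked in with a fully methylated lambda-phage DNA internal control", is fragmented and ligated to adaptors, and is then halved. One half is the total input; the other is enriched for methylated DNA.
- MI is (H_E/H_T)/(S_E/S_T). Here "H_E and H_T are the number of reads mapping to the prostate cancer specific hypermethylated regions in the enriched and total input fractions respectively". The spike-in counts S_E and S_T are defined likewise.
- The 350 regions are described as hypermethylated in prostate cancer and not in the normal tissues examined.
- On interpretation, "this MI score is related to the amount of methylated DNA" from those regions. The lambda-phage DNA is called a quantitation standard.
- SR counts rearranged read pairs in the total input per million overall reads, and "will provide a parallel measure of the amount of DNA containing genomic rearrangements".
- On use, "the kinetics for these measures will be determined at the timepoints collected and compared with PSA values". The exploratory objective in Section 2.0 adds clinical response to the comparison.

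Samples are taken before and after androgen suppression, and at about 4 weeks and 6 months after the implant (Section 4.5 calendar). The text gives no spike-in quantity, no total cell-free DNA measure and no per-mL version of either score.

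**The concern.** PSA is a concentration. A score set beside it over time, and described in terms of amount, will be read as though a fall means less tumour DNA. A fraction can also fall because its denominator has grown. Biopsy and brachytherapy come between the second and third samples, and androgen suppression between the first and second, so a constant background of normal DNA cannot simply be taken for granted. The plan names no quantity that would check it. SR offers no independent protection, because its denominator is also all the DNA in the sample. What is at stake is how a change in MI or SR is interpreted in the exploratory analysis.

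**Working it through.** The plan gives a formula but no numerical MI value, so there is no figure to reproduce. The check is algebra on the plan's definitions, followed by assumed counts.

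**Symbols.** M = methylated tumour copies at the 350 regions; U = unmethylated normal copies there; S = spike-in copies; e = capture efficiency; b = capture of unmethylated DNA; r = b/e; d_E and d_T = depth factors of the two halves. None of these values is in the documents.

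**Read counts.** The spike-in goes in before the split, so both halves carry it:

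- H_E = d_E(eM + bU)
- H_T = d_T(M + U)
- S_E = d_E·e·S
- S_T = d_T·S

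**Result.** MI = (M + rU)/(M + U). S, d_E and d_T drop out. With r = 0, e drops out too, and MI = M/(M + U).

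Rearranging the plan's formula gives MI = (H_E/S_E)/(H_T/S_T). MI is therefore the ratio of two spike-calibrated quantities:

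- H_E/S_E = (M + rU)/S
- H_T/S_T = (M + U)/S

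The amount information is in the four counts and is lost only when the ratio is taken.

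**Illustration, r = 0, S = 1,000:**

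| Scenario | M | U | MI | H_E/S_E | H_T/S_T |
|---|---|---|---|---|---|
| Baseline | 100 | 900 | 0.100 | 0.100 | 1.00 |
| Normal DNA doubled | 100 | 1,800 | 0.053 | 0.100 | 1.90 |
| Normal DNA tripled | 100 | 2,700 | 0.036 | 0.100 | 2.80 |
| Normal DNA halved | 100 | 450 | 0.182 | 0.100 | 0.55 |
| Tumour DNA halved | 50 | 900 | 0.053 | 0.050 | 0.95 |
| Both doubled | 200 | 1,800 | 0.100 | 0.200 | 2.00 |

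Rows two and five have the same MI (100/1,900 = 50/950) and differ clearly in the last two columns. In the last row tumour DNA has doubled and MI has not moved.

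**Range over the starting fraction, normal DNA doubled, r = 0.** From 1%: 10/1,000 = 0.010 to 10/1,990 = 0.005, a 50% fall. From 10%: 0.100 to 0.053, a 47% fall. From 50%: 500/1,000 = 0.50 to 500/1,500 = 0.33, a 33% fall.

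**SR.** Suppose rearranged reads come only from tumour DNA and spike-in reads are a negligible part of the total. SR is then proportional to the tumour share of all DNA. A share going from 100/1,000 to 100/1,900 lowers SR by the same 47%. Rearranged reads divided by S_T would not change.

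**Sensitivity of H_E/S_E to background capture, normal DNA doubled:**

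| M, U at baseline | r | MI | (H_E/S_E) × S |
|---|---|---|---|
| 100, 900 | 0.01 | 0.109 to 0.062 (−43%) | 109 to 118 (+8%) |
| 100, 900 | 0.05 | 0.145 to 0.100 (−31%) | 145 to 190 (+31%) |
| 1, 99 | 0.01 | 0.0199 to 0.0150 (−25%) | 1.99 to 2.98 (+50%) |

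In the last row the calibrated amount moves more than MI, and in the opposite direction. The calibrated total, (H_T/S_T) × S, goes from 100 to 199 and would reveal the cause.

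**The case against.** The strongest reply is that a fraction is a defensible choice. It cancels extraction recovery and urine dilution. The spike-in is added to DNA already purified, so a spike-calibrated amount does not correct for recovery, and an amount per mL of urine varies with how dilute the urine is. That stands, and together with the background-capture results it is why H_E/S_E should not take MI's place.

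The wording on MI is also soft: being related to an amount is not a promise of copies per mL, and at constant background MI does follow the tumour amount. That stands as well, but the plan neither states nor checks the condition, and the sentence on SR is firmer.

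Three stronger readings are tempting and are not supported:

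- *That the spike-in does nothing.* Only its quantity cancels; S_E/S_T still corrects for capture efficiency and relative depth.
- *That the implant will raise normal DNA and produce a false response.* Nothing in the documents says that background rises, by how much, or that a rise would last to 4 weeks or 6 months. A fall would push MI the other way.
- *That the whole therapeutic-response question rests on these scores.* Section 5.2.2 attaches tracking of response to the separate COMPARE-MS locus panel. MI and SR are compared with PSA there, and Section 2.0 mentions clinical response only in general terms.

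The planned dilution series is described as exploring accuracy and precision, not background that changes within a patient. The missing figures and cited method papers may specify the spike-in quantity or a DNA measurement; the text available does not.

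**Conclusion.** The point holds in a limited form. By the plan's own definitions MI is a capture- and depth-corrected methylated fraction and SR is a relative frequency, while the text presents both in terms of amount. A change in either can reflect tumour DNA, background DNA or both, and the planned scores alone cannot say which.

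The size is unknown. Doubling normal DNA lowers MI by 33% to 50% for starting fractions of 50% down to 1%, but the counts, the doubling and the zero background capture are all assumptions. The conclusion that the spike-in quantity cancels needs only that it is added before the split, as the plan describes, and that read counts are proportional to copies.

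This is an inexpensive improvement, not a defect in the trial's main question. Sampling for these scores needs separate optional consent, detection feasibility is itself part of the exploratory aim and is served by a fraction, and the gammaH2AX endpoint is untouched.

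**What to change.** In Section 5.2.2:

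1. Keep MI and SR as defined, but describe them as relative measures: a methylated fraction, and a frequency of rearranged reads.
2. Add a fixed, recorded quantity of spike-in to DNA from a recorded volume of plasma or urine.
3. From the same reads, report beside MI the spike-calibrated amount H_E/S_E and the spike-calibrated total at the regions H_T/S_T. Report rearranged reads scaled to S_T beside SR. Multiplying by spike-in copies and dividing by volume gives per-mL values for comparison with PSA.
4. State in advance that a change in MI is read as response only when a change in background, shown by H_T/S_T, does not explain it.

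The cost is one recorded laboratory quantity and a few more exploratory summaries; no new assay is needed. State the limits with the results: H_E/S_E is sensitive to background capture at low tumour fraction, extraction recovery is not corrected, and per-mL urine values depend on urine dilution. The change is best made before samples are processed, because an unrecorded spike-in quantity may not be recoverable later.
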